1.1. Background and rationale for the study

Knee pain is experienced by 33% of adolescents¹, and the prognosis of knee pain is often unfavorable, with approximately 50% of adolescents still reporting knee pain after 1 or 2 years^{1,2}. Common child and adolescent knee pain includes a variety of conditions (e.g. patellofemoral pain, patella tendinopathy, fat pad impingement, Osgood-Schlatter and Sinding-Larsen-Johansson disease), with specific treatments provided (e.g. education, activity modification, flexibility and strengthening exercises, cryotherapy, orthoses, patellar taping, medications) depending on the condition^{3,4}. Knee pain is linked to both health and social consequences³. Children and adolescents with knee pain are more likely to reduce their sport participation, with following issues regarding the overall health (e.g. poor cardiovascular health, higher adiposity, impaired sleep)^{1,5-8}, to have a higher rate of school absence^{6,9} and to be affected in the choice and performance of future work activities^{10,11}. Knee pain in children and adolescents has also an economic impact, which include both direct (e.g. primary care visits, community services use, medication use) and indirect (e.g. parental productivity work loss and days off work) costs^{12,13}. Knee pain in childhood and adolescence may also persist in adulthood; previous studies have shown that a high proportion of them experience recurrence of symptoms over up to 20 years of follow-up^{14,15}, and adolescent knee pain might be a precursor of adult knee conditions such as knee osteoarthritis¹⁶⁻¹⁹. While there is a body of research on adult knee pain²⁰⁻²², less is known in children and adolescents, who are a distinct population compared to adults with different physiology and psychosocial development^{5,23}. Potential prognostic factors for knee pain identified in previous studies conducted in adolescents include female gender, high leisure time sport

participation, low health-related quality of life, high baseline frequency of knee pain ². A proportion of children and adolescents with knee pain will consult the general practitioner because of their condition; previous research has shown an annual consultation prevalence for knee pain in children and adolescents of 119 ²⁴ - 200 ²⁵ per 10,000 registered persons.

Once patients have consulted for their knee pain, general practitioners are left with the difficult task of figuring out how their patient's condition can progress (i.e. if the patient will get better or not) in order to provide them with the best care ^{26,27}. This include avoiding overdiagnosis (i.e. identification of a pathological state which will not result in a future poor outcome but might lead to unnecessary over-medicalization) and taking into account the patient's entire biological, psychological and social context ²⁷.

General practitioners can be aided in the decision process by prognostic tools, which are tools that are used to stratify patients and match them to specific treatments depending on their risk of recurrence or persistence of a condition. This type of tools can help clinicians to identify subgroups of patients with different risk of recurrence or persistence of a pain condition depending on a prognostic score derived from a combination of individual prognostic factors ²⁸.

Examples of prognostic tools that have already been developed include the Keele STarT Back Screening Tool (SBST) for back pain in adults ²⁹ or the Pediatric Pain Screening Tool (PPST) for general pediatric pain ²⁸. However, a prognostic tool to be used specifically for the prognosis of knee pain in children and adolescents in primary care has not been developed yet, as the PPST included physical and psychosocial items that can be applied to general musculoskeletal and non-musculoskeletal pain conditions and it was validated in tertiary care settings ^{28,30}. Therefore, the development of a pediatric knee pain prognostic tool will fill this gap and will enable general practitioners to provide stratified care by tailoring the best targeted treatment to patients with

knee pain according to the category of risk. In summary, the development of a prognostic tool for child and adolescent knee pain within a primary care setting is important for three reasons:

1. First, primary care is the place where the majority of health care is delivered ³¹, and consequently research carried out within this setting has the potential to have a significant impact in real-life.
2. Second, a prognostic tool developed for knee pain will include items about factors that are specific to the prognosis of knee pain (e.g. pain duration, previous history of knee pain) and therefore would be more sensitive than other more general pediatric pain tools, such as the PPST. This is important considering that misclassification of patients might potentially lead to undertreat those misclassified as low-risk and overtreat those misclassified as high-risk ³².
3. Third, the subgroup of patients who refer to primary care is usually characterized by a different severity of symptoms compared to general population, second or tertiary care samples, as proposed by the iceberg theory of disease ³³⁻³⁵, and it is recommended that prognostic tools are validated in different care settings ³⁶. Therefore, this research has the opportunity to provide information on the predictive ability of a prognostic tool in primary care compared to studies carried out within other samples of care settings, as it has previously been observed a difference in the efficacy of risk prediction potentially because of differences in patients case mix ³⁷.

1.2. Aim of the study

The overall aim of this study is to develop and test a prognostic tool for knee pain in children and adolescents to be used in general practice.

1.3. Importance of this study

The importance of this study lies in the fact that the development of a prognostic tool for children and adolescents with knee pain will allow general practitioners to categorize them according to their category of risk and consequently provide them the best targeted treatment.

1.4. Specific objectives of the study

- 1) Identification of prognostic factors for knee pain in children and adolescents**
 - a) Review of prognostic factors for knee pain in children and adolescents from current literature**
 - b) Selection of prognostic factors to be included in the prognostic tool**
- 2) Development of a prognostic model**
 - a) Development of the questions to be included in the prognostic tool**
 - b) Discussion about the questions wording with GPs**
 - c) Identification of the most suitable form to deliver the prognostic tool**
- 3) Piloting the prognostic tool and recruitment procedures**
 - a) Testing the prognostic tool at the general practices**
 - i) Assess time taken to use the prognostic tool**

- ii) Assess quality/acceptability of the prognostic tool (e.g. content of the questions and domains included, acceptability and understanding of the questions used, acceptability of the delivery of the tool, face validity, construct validity, criterion validity)
- b) Assess participants' recruitment processes
 - i) Assess baseline response (e.g. ratio between children who participated in the study over all those who consulted for knee pain as recorded with codes for consultation) and reasons for non-participation
 - c) Improvement of the prognostic tool and of the recruitment procedures
- 4) Recruitment of children and adolescents and collection and analysis of the data
 - a) Description of the sample characteristics
 - b) Assess the predictive ability of the prognostic tool
 - i) Sensitivity
 - ii) Specificity
 - c) Assess baseline response and reasons for non-participation
 - d) Assess loss to follow-up and reasons for dropping out of the study where possible
- 5) Cost-effectiveness of the study (optional depending on time availability)
 - a) Assess the workload for GPs, researchers and administrative staff
 - b) Assess the time needed to deliver the tool in general practice and identification of alternative solutions to deliver the tool (e.g. by using iPads etc)
 - c) Assess satisfaction of the participants and general practitioners with the study
 - d) Evaluation of the effectiveness and suitability of this study in light of the resources available in general practice

1.5. Study design

Prospective cohort study. Data will be collected at baseline through a questionnaire delivered at the general practice if the primary recruitment strategy will be applied. Otherwise, the baseline collection of the data will occur through a questionnaire home-mailed or delivered through a survey internet link if a strategy of recruitment through social media will be applied (please see section 2.7.2 for a description of the recruitment strategies). Outcomes will be collected by questionnaires either self-reported or parent-reported (collected through e-mail or text messages) at follow-up.

2. Methods

2.1. Study Setting

The aim is to collect data from general practices based in Denmark (with a potential complementary recruitment occurring through social media). For logistic reasons the recruitment will initially focus on large practices (populations around 10.000 each). However, smaller practices may be included too. For a calculation of the number of practices required to carry out the project please see section 2.5.

2.2. Participants and eligibility criteria

Children and adolescents who consult their general practitioner because of their knee pain (of both traumatic and non-traumatic origin) during a period of recruitment of 6 months (starting in July 2019) are eligible for inclusion.

2.2.1. Inclusion criteria:

- Age between 8 and 19 years old. The age of 8 is considered to be the lowest age for the children to be able to complete a pain questionnaire or a pain chart without adult guidance³⁸ (provided that the questions are properly worded by taking into account the age-related cognitive abilities^{39,40}), and the age of 19 is defined as the upper limit for the period of adolescence by the World Health Organization⁴¹.

2.2.2. Exclusion criteria:

- Age below 8 years old or over 19 years old
- Consultation for musculoskeletal pain only in a body region different from the knee

- Pain originated by different conditions (e.g. cancer, infections)
- Child is vulnerable (e.g. he/she has experienced a recent trauma and the distress may have an impact on the self-report making it not valid)³⁹
- Inability to take part to the study because of inability to understand or comply

2.3. Outcome measures

The primary outcome measure will be the recurrence/persistence of activity-limiting knee pain (i.e. yes/no pain that is limiting activities in the same knee) at 3-month follow-up⁴². Participants will also be asked about continuity of their knee pain (i.e. “how long have you been free of knee pain?”), to enable the distinction between recurrence (on/off knee pain episodes between baseline and follow-up) and persistence (continuous knee pain from baseline to follow-up) of knee pain. A secondary outcome measure that will be collected is the recurrence/persistence of activity-limiting knee pain at 6-month follow-up.

Previous studies have shown an effect of the treatment received on the change in risk group for the recurrence/persistence of pediatric pain⁴³ and on the change in pain and function⁴⁴. Therefore, an additional outcome measure that might potentially be assessed include the treatment effectiveness on the recurrence/persistence of knee pain (provided that there will be the possibility to collect data on the treatment given). For practical reasons, it might be considered assessing this additional outcome on a subsample of children and adolescents.

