3. Har du ondt i det ene knæ eller begge knæ?	 Kun det ene knæ (højre knæ)  Kun det ene knæ (venstre knæ)  Begge knæ
4. Hvor lang tid har du haft ondt i knæet? Hvis du har ondt i begge knæ skal du svare ud fra det knæ hvor smerterne har varet længst	 under 3 måneder  3–6 måneder  6–12 måneder  mere end 12 måneder (hvor mange år? _____)
5. Hvordan startede dine knæsmerter? Hvis du har ondt i begge knæ skal du svare ud fra det knæ hvor smerterne har varet længst	 Kom pludseligt (f.eks. da jeg fik en skade)  Kom gradvist (f.eks. langsomt over en længere periode)
6. Hvor ofte oplever du dine knæsmerter? Hvis du har ondt i begge knæ skal du svare ud fra det knæ hvor smerterne har varet længst	 Sjældent  Månedligt  Ugentligt  Mere end en gang om ugen  Næsten dagligt
7. Har du ondt andre steder i kroppen som gør at du ikke kan deltage i dine normale aktiviteter (leg i skolegården, sport og lignende)? I dette spørgsmål menes andre steder end knæet	 Nej  Ja. Marker venligst hvor. Du må gerne afkrydse mere end et område:  Hovedet  Ryg eller nakke  Skulder  Albuen  Håndled eller hånden  Underbenet  Låret  Bækkens (badebuksområdet)  Ankel, hælen eller fodden  Andet (_____)

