8. Under hver overskrift bedes du sætte kryds i DEN kasse, der bedst beskriver hvordan dine knæsmerter påvirker de ting du laver på en normal dag (f.eks., gå i skole, hobbyer, sport, være sammen med venner eller familie) Hvis du har ondt i begge knæ skal du svare ud fra det knæ hvor smerterne har varet længst	 Jeg har ingen problemer med at udføre mine sædvanlige aktiviteter  Jeg har lidt problemer med at udføre mine sædvanlige aktiviteter  Jeg har nogle problemer med at udføre mine sædvanlige aktiviteter  Jeg har store problemer med at udføre mine sædvanlige aktiviteter  Jeg kan ikke udføre mine sædvanlige aktiviteter
9. Hvor enig er du i dette udsagn "Når jeg har ondt, er det forfærdeligt og jeg tror aldrig det bliver bedre" Sæt kryds i den kasse som bedst beskriver hvordan du har det i dag. Ængstelig/deprimeret svarer til at være ked af det (det handler om hvordan du har det, og ikke nødvendigvis på grund af dine smerter)	 Overhovedet ikke  Lidt  I nogen grad  Meget  Rigtig meget  Jeg er ikke ængstelig eller deprimeret  Jeg er lidt ængstelig eller deprimeret  Jeg er i nogen grad ængstelig eller deprimeret  Jeg er meget ængstelig eller deprimeret  Jeg er ekstremt ængstelig eller deprimeret
10. Har din mor eller stedmor ofte ondt i kroppen? (dette kan både være ondt i hovedet, ryggen, skulderen eller andre steder) Har din far eller stedfar ofte ondt i kroppen? (dette kan både være ondt i hovedet, ryggen, skulderen eller andre steder)	 Nej  Ja  Nej  Ja
11. Hvor mange gange per uge deltager du typisk i sport (udover idræt i skolen)? Hvilken type sport? (feks håndbold, fodbold, svømning, løb). Du må gerne skrive mere end en sport.	 Aldrig  1 gange/uge  2 gange/uge  3 gange/uge  4 gange/uge  5 gange/uge  6 gange/uge  7 eller flere gange/uge (_____)

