12. Har du røget cigaretter i de sidste 4 uger?	 Nej  Ja
13. Hvor enig er du i dette udsagn "Jeg har problemer med at sove" (det behøver ikke nødvendigvis være på grund af smerter)	 Aldrig  Næsten aldrig  Nogle gange  Ofte  Næsten altid

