2.8.2. Collection of data during follow-up

Data will be collected during follow-up from the children or parents through a questionnaire email-based or to be completed by text messages depending on the participants' preference. The questionnaire will include questions about pain characteristics (e.g. severity of pain, period free of knee pain, disability and activity limitations due to pain ^{42,48}) and about who is the person replying to the questionnaire (child alone/parent alone/child together with the parent). These questions will be taken from previously validated pain questionnaires or pain scales. Data collected at 3-month follow-up will be used to assess the primary outcome of the study, and data collected at 6-month follow-up will be used to assess the secondary outcome. In order to limit loss to follow-up, an e-mail/text message reminder will be sent to participants if they do not complete the follow-up questionnaire within one week from the day when they are supposed to reply. A second reminder

will be sent one week after the first reminder if they still will not have completed the follow-up questionnaire.

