2.14. Impact/dissemination

The present study will provide data on the prognosis for knee pain in children and adolescents who present to primary care. In addition, this study will provide data on the usability of a prognostic tool to allocate children and adolescents to a category of risk for knee pain recurrence and consequently provide them with the best targeted treatment. The study results will be disseminated at scientific conferences and through appropriate scientific journals. In addition, general practitioners, children and parents participating into the study will be regularly provided with feedback about the ongoing study.

Examples of papers that might be developed from this study (provisional names are provided):

- 1) The Adolescent Knee Pain (AK-Pain) prognostic tool: protocol for a prospective cohort study
- 2) Stability of prognostic factors for knee pain collected with a questionnaire in general practice
- 3) The development of a prognostic tool for knee pain in children and adolescents in general practice
- 4) Effect on the treatment delivered on the knee pain prognosis on a subsample of the participants recruited in the AK-pain project

3. Protocol amendments

Potential protocol amendments might occur during the prognostic tool piloting and development stage. Protocol amendments will be disseminated to proper scientific journals.

4. Declaration of interest

The study's investigators have no conflicts of interest to declare.

5. Access to data

The final dataset will be accessed by [name], [name], [name] and [name].

References

doi:10.1177/0363546515622456
3. Houghton KM. Review for the generalist: Evaluation of anterior knee pain. *Pediatr Rheumatol.* 2007;5:1-10. doi:10.1186/1546-0096-5-8
5. Rathleff MS. Patellofemoral pain during adolescence: Much more prevalent than appreciated. *Br J Sports Med.* 2016;50(14):831-832. doi:10.1136/bjsports-2016-096328

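### The pain-free-duration question in section 2.3 cannot separate recurrence from persistence in a child who is in pain when answering at 3 months

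*Combined protocol and SAP*

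**What the plan says.** Section 2.3 sets the primary outcome as a single yes/no: activity-limiting pain in the same knee at 3 months, with recurrence and persistence taken together. The same outcome at 6 months is secondary. The section then says that participants will be asked about the continuity of their pain. It introduces one question with an i.e., "how long have you been free of knee pain", and states the purpose: "to enable the distinction between recurrence (on/off knee pain episodes between baseline and follow-up) and persistence". Persistence is defined there as pain that continues throughout the interval.

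Section 2.8.2 describes the follow-up questionnaire by example: "severity of pain, period free of knee pain, disability and activity limitations due to pain", together with who gave the answers. It adds: "These questions will be taken from previously validated pain questionnaires or pain scales".

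Step 3 of section 2.10 models recurrence and persistence as one dichotomous outcome. The close of 2.10 mentions that the prognostic tool might also be given at 3 months, but only as a possibility and in order to track changes of risk group.

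**The concern.** The two courses that 2.3 wants to tell apart differ in what happened between baseline and follow-up. The question offered for this looks back only as far as the most recent pain. In a child who is in pain when answering, that look-back has length zero, and the earlier weeks are not recorded. These are largely the children for whom the distinction is wanted, because the outcome is pain at follow-up.

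At stake is a description that the plan says it will be able to give: how much of the combined outcome is pain that returned and how much is pain that never went away. If the form holds nothing beyond the named items, that history cannot be reliably reconstructed once follow-up has closed.

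**Working it through.** The plan gives no figure on this point, so there is none to reproduce. The check is to list possible pain courses and see what each item would record.

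**Inputs.** All children recruited in general practice are consulting for knee pain (2.2). The definitions and the question come from 2.3, and the other follow-up items from 2.8.2. Three months is taken as 91 days. The courses below are invented for illustration.

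**Step 1: the existing question at 3 months.** Answer = length of the pain-free run that is still going on at day 91. The last column shows the longest pain-free spell since baseline.

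| Course from baseline to day 91 | Meaning under 2.3 | Answer to existing question | Longest pain-free spell |
|---|---|---|---|
| A. Pain throughout | Persistence | 0 | 0 |
| B. Pain-free days 20 to 80, then pain again | Recurrence | 0 | 80 − 20 = 60 |
| C. Pain-free days 10 to 30 and 50 to 70, then pain again | Recurrence | 0 | 30 − 10 = 20; 70 − 50 = 20 |
| D. Pain stops at day 31 and stays away | Neither | 91 − 31 = 60 | 60 |

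The existing question separates D from the rest but gives the same answer for A, B and C. The longest spell separates A from B and C, but gives the same value for B and D. The two items together separate persistence, recurrence and resolution.

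**Step 2: the other named items.** Severity, disability and activity limitation describe how bad the pain is. None records whether it stopped and came back. The identity of the respondent is no help either.

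**Step 3: combining visits at 6 months.** Among children in pain at 6 months:
- pain-free at 3 months: recurrence is established;
- in pain at 3 months as well: unresolved, because the answer is zero at both visits.

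This does nothing for the 3-month time point, which is the primary one.

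**Step 4: repeating the baseline tool at 3 months.** Item 4 of the tool asks how long the knee has hurt, and its lowest category is under 3 months. That answer from a child in pain at 3 months would suggest a new episode. A child whose pain had come back could equally count from the first onset. Item 6, "Hvor ofte oplever du dine knæsmerter", asks about frequency, not about interruption since baseline. The route is conditional and gives at best a coarse indication.

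**Step 5: how many children.** The documents give no 3-month rate. Purely for illustration, suppose that 300 children (the larger recruitment target in 2.5) answered, and that 30%, 50% or 70% were in pain when answering. Then 0.30 × 300 = 90, 0.50 × 300 = 150 or 0.70 × 300 = 210 could not be classified by this question. The 50% echoes the background figure in 1.1, which refers to 1 or 2 years and not to 3 months.

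**The case against.** The strongest reply is that the split carries no weight in the analysis. The primary outcome is a combined yes/no, and no regression, ROC, cut-off, sensitivity or likelihood-ratio step in 2.10 uses it. That is correct, and it limits the point to a descriptive one.

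A second reply is that the form cannot be seen. The baseline tool is in Danish, so the English wording in 2.3 may be a gloss. Section 2.8.2 lists content only as examples, and its mention of a pain-free period could cover any spell since baseline. This stands as a limit: nothing here shows that the fielded form lacks a suitable item. But 2.3 gives the wording with an i.e., and that wording asks about the current spell. If any spell is meant, the text needs to say so.

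A third reply is that other routes exist: the two visits together, or a repeat of the tool. The first works for some children at 6 months and the second is conditional, so neither makes the statement in 2.3 true at 3 months.

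A child with the outcome could also report a few pain-free days, if the outcome question looks back over a period. Section 2.3 states no such period. An answer above zero would show that pain was not continuous up to that day, which is why the point is confined to children in pain when answering.

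Finally, the proposed item asks for recall from children as young as 8. That cost is real and is set out with the fix.

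**Conclusion.** The point holds in a limited form. Section 2.3 attributes to one question a property that it does not have as worded: at 3 months it cannot tell returned pain from unbroken pain in a child who is in pain when answering. At 6 months the gap remains for children in pain at both visits. The conclusion rests on the wording in 2.3 and on the items named in 2.3 and 2.8.2. How many children it concerns is unknown.

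Three stronger readings are tempting and not supported.
- A reader might infer that the primary outcome or the prognostic model is compromised. It is not, because both use the combined outcome.
- A reader might infer from 2.14, which speaks of a "allocate children and adolescents to a category of risk for knee pain recurrence", that the risk groups will be mislabelled, or from the shorter outcome wording in 2.10 that a different outcome will be modelled. Both are ordinary shorthand. Section 1.1 uses recurrence or persistence for the same idea, and step 6 of 2.10 refers back to the primary and secondary outcome.
- A reader might try to express the loss as a share of the follow-up days by borrowing a look-back period from the baseline tool. The explicit periods there belong to the mood and smoking items, and days not covered are not children misclassified.

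**What to change.** Keep the existing question, since it records the current pain-free run. Add one short item at both follow-ups: whether there was any period without knee pain since the last completed questionnaire and, if so, how long the longest one was. Tying it to the last completed questionnaire covers children who did not return the 3-month form.

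In 2.3, before follow-up data are seen, state the minimum pain-free length that counts as an interruption. This is needed because all five answers to baseline item 6, from rarely to almost daily, allow days without pain. With no minimum, nearly every child could count as having on/off pain. The length is for the investigators to choose; the documents give no basis for a particular value.

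In 2.8.2, note that this item may not come from a validated scale, as an exception to the commitment made there.

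The cost is one extra item per follow-up and a few lines of text, with no added contacts or participants. The downside is recall over about 3 months, or 6 if the 3-month form is missing.

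If the item cannot be added, for instance because follow-up has closed, remove from 2.3 the statement that recurrence and persistence can be distinguished. That costs nothing and leaves the primary outcome as it is.
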